10.1 Adverse Events

Verbatim descriptions of AEs will be coded using MedDRA (Version to be delineated in the CSR). Summary tables will be provided for all treatment-emergent adverse events (TEAEs) but all AEs will be provided in a listing. A treatment-emergent AE is defined as any AE that newly appeared, increased in frequency, or worsened in severity on or after the initiation of active test article. An AE is considered treatment emergent if the AE start date and time is on or after the start date and time of the first infusion of active test article. If time of the AE is missing and it occurred on the same date as the first infusion of active test article, the AE will be defined as treatment emergent. If the start date of the AE is partial or missing and it cannot be determined if the AE occurred prior to or after the first dose of test article, the AE should be defined as treatment emergent.

An overall summary of AEs will include the number of subjects who experienced at least one AE of the following categories: any AE, any TEAE, any drug-related TEAE, any severe TEAE, any serious TEAE, any drug-related SAE, any serious TEAE leading to death, any TEAE leading to premature discontinuation of test article, any TEAE leading to premature discontinuation from the study, any TEAE leading to dose interruption of test article, and any serious TEAE leading to premature discontinuation of test article.

The number and percentage of subjects reporting a TEAE in each treatment group will be tabulated by system organ class and preferred term; by system organ class, preferred term, and severity (mild, moderate, and severe); and by system organ class, preferred term, and relationship (unrelated or related to test article). The incidence of TEAEs will be summarized by preferred term and treatment group, sorted by decreasing frequency in the omadacycline group, for all TEAEs, related TEAEs, serious TEAEs, and TEAEs leading to study drug discontinuation. The number and percentage of subjects reporting a TEAEs representing administration/infusion site reaction (based on the appropriate MedDRA higher level term) will be tabulated by treatment group, preferred term and severity (mild, moderate, and severe). The incidence of serious TEAEs, TEAEs leading to premature discontinuation of test article, and TEAEs leading to a dose interruption of test article will be summarized by system organ class and preferred term. For all analyses of TEAEs, if the same AE (based on preferred term) is reported for the same subject more than once, the AE is counted only once for that preferred term and at the highest severity and strongest relationship to test article.

TEAEs occurring (ie, with a start date and time) during the time period subjects are on treatment, and separately for the time period subjects are on iv and po test article will be summarized by system organ class and preferred term.

In addition, all AEs (including non-TEAEs), serious TEAEs, TEAEs leading to discontinuation of test article, and TEAEs leading to dose interruption of test article will be provided in listings by treatment group, study site, subject, verbatim term, MedDRA system organ class and preferred term, start and end date, seriousness flag, severity, relationship to test article, relationship to study protocol, action taken with test article, non-test article action taken and outcome.

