## 7.6 Test Article Administration

### 7.6.1 Intravenous Treatment Phase

The iv-treatment phase (minimum 2 days) will follow a double-blind, double-dummy design for omadacycline and moxifloxacin. Infusions of 100 mg omadacycline or matched placebo will be administered continuously, without interruptions, over 30 minutes ( $\pm$  5 minutes). On Day 1, if QD dosing is selected, the 200 mg infusion of omadacycline or matched placebo will be administered continuously, without interruptions, over 60 minutes ( $\pm$  5 minutes). On Day 1 of iv treatment, if twice a day dosing (BID) was selected, subjects on the moxifloxacin treatment arm will receive an additional placebo infusion to match the t = 12 h infusion. Infusions of moxifloxacin or matched placebo will be administered continuously, without interruptions, over 60 minutes ( $\pm$  5 minutes).

The first dose of test article should be administered within 4 hours of randomization. All infusion start and stop times are to be recorded in the source documents and on the eCRF. Because the color of the test article and placebo infusions are different, all infusion bags and iv tubing will be covered with materials provided by the sponsor (as described in the Pharmacy Manual) so that

subjects and blinded study personnel will not know the identity of the test article being administered. Subjects in each study arm will receive the same infusion volumes with the same blinded administration instructions. All iv infusions will be administered by qualified blinded personnel. However, unblinded personnel may administer the iv infusions provided they will not be performing any efficacy assessments. If gravity administration is not the standard of care, then an infusion pump may be used. If an infusion pump is used, then an unblinded administrator will be required. Subjects may receive iv treatment in certain outpatient centers in circumstances where the principal site investigator has identified that sufficient resources are available to complete all study procedures as defined in the protocol and the sponsor or sponsor's designee has reviewed and approved the process for outpatient iv test article administration.

Please refer to Table 1 for more detail on the Treatment regimens for iv dosing.

Infusion Timepoint a	Infusion Number	Omadacycline Arm b,c	Moxifloxacin Arm b,c
	1	omadacycline 100 mg in 100 mL NS	100 mL NS placebo

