### 8.21 Recording and Reporting

A subject's AEs and SAEs will be recorded and reported from the signing of the ICF to the time of the Final Follow-up assessment. The investigator must instruct the subject to report AEs and SAEs during this time period. Reports of death after the last contact with the subject will be reported to the sponsor and additional information relative to the cause of death will be sought and documented.

All AEs and SAEs must be recorded on source documents. All AEs and SAEs for subjects who receive a treatment assignment will be recorded in the eCRFs.

The investigator must follow-up as medically necessary on all AEs and SAEs until the events have subsided, the condition has returned to Baseline, or in case of permanent impairment, until the condition stabilizes.

AEs should be based on the signs or symptoms detected during the physical examination and on clinical evaluation of the subject. In addition to the information obtained from those sources, the subject should be asked the following nonspecific question: "How have you been feeling since your last visit?" Whenever possible, AEs should be reported as a diagnosis rather than individual signs and symptoms. If a definitive diagnosis is not possible, the individual signs and symptoms should be recorded using standard medical terminology.

If an AE requires a surgical or diagnostic procedure, the illness leading to the procedure should be recorded as the AE, not the procedure itself.

Death should be recorded in the eCRF as an outcome of an AE. Any unanticipated risks to the subjects must be reported promptly to the IRB/IEC/REB.

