#### 8.21.3 Assessment of Severity

The severity (or intensity) of an AE will be classified using the following criteria:

- Mild: These events are usually transient, require minimal or no treatment, and do not interfere with the subject's daily activities.
- Moderate: These events result in a low level of inconvenience or concern with the therapeutic measures. Moderate events may cause some interference with normal functioning but pose no significant or permanent risk of harm.

• Severe: These events interrupt a subject's usual daily activity and may require systemic drug therapy or other treatment. Severe events are usually incapacitating.

Changes in the severity of an AE should be documented as a new event to allow an assessment of the duration of the event at each level of intensity to be performed.

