# **9 STUDY ACTIVITIES**

#### 9.1 Screening Phase

The Screening visit should be completed within a 24-hour period prior to randomization. The Screening procedures will be used to establish subject eligibility and baseline characteristics for each subject. Following the signing of an ICF, the site staff will collect/perform the assessments detailed in Appendix 1.

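### Because every change in AE severity opens a new record, dating by record start puts easing iv-onset AEs in the oral-period table and can flag an improving pre-dose AE as treatment-emergent

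*SAP*

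**What the plan says.** **How records are created.** Protocol 8.21.3: "Changes in the severity of an AE should be documented as a new event to allow an assessment of the duration of the event". The stated purpose is to measure duration separately for every grade of severity. The sentence is not limited to worsening. Protocol 8.21: "A subject's AEs and SAEs will be recorded and reported from the signing of the ICF to the time of the Final Follow-up assessment", so AEs with onset before the first dose are collected.

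**How treatment emergence is decided.** SAP 10.1 first defines a TEAE as "any AE that newly appeared, increased in frequency, or worsened in severity on or after the initiation of active test article". The next sentence gives the working rule: "An AE is considered treatment emergent if the AE start date and time is on or after the start date and time". Its reference point is when active drug was first infused, and it makes no comparison of severity. Protocol 12.9.1 also defines a TEAE by start date and time only.

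**How the iv and po periods are assigned.** SAP 10.1 summarizes "TEAEs occurring (ie, with a start date and time) during the time period subjects are on treatment", and does the same separately for the time on iv and the time on po test article.

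**How repeats are handled.** In TEAE analyses, SAP 10.1 counts a preferred term once per subject, at the greatest severity and closest relationship.

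**The concern.** The recording rule and the analysis rule do not fit together. A record opened because an AE has eased carries the date of the easing as its start. The SAP treats that date as an onset, both for treatment emergence and for period.

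Two planned counts are exposed. The po-period table can show AEs that began on iv, for example an infusion-site reaction that lessens after the switch. The TEAE tables can gain events that predate treatment and got better on it. For easing events the period error runs in one direction, because Protocol 7.6.5 has all randomized subjects start with at least 2 days of iv and oral drug can only follow.

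The protocol splits records so that duration at each intensity can be assessed, but the SAP plans no such analysis. The split therefore brings the artefact into the tables without serving its stated purpose.

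**Working it through.** The plan states no figure to reproduce. The check applies the written rules to each type of record, then sizes the effect under stated assumptions.

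**1. Rules applied to each case**

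| Case | SAP definition | Start-date rule | Effect of once-per-term rule | Result as written |
|---|---|---|---|---|
| Onset before first dose, improves after it | Not a TEAE | Second record is a TEAE | None: the earlier record is not a TEAE, so there is nothing to merge with | Spurious TEAE |
| Onset on iv, eases on oral drug | TEAE | Both records are TEAEs | Merges them in the overall tables, but not across the separate iv and po tables | Counted in both the iv and the po table |
| Onset after first dose, eases within the same period | TEAE | Both records are TEAEs | Merges them at the highest severity | Counted once, correctly |

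**2. Width of the pre-dose window**

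Protocol 9.1: "The Screening visit should be completed within a 24-hour period prior to randomization". Protocol 7.6.1: "The first dose of test article should be administered within 4 hours of randomization". So 24 h + 4 h = about 28 h at most between consent and first dose.

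**3. Constructed example**

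Five subjects, hours from first dose, oral switch set at 72 h. Linked means that only a first record, or one above the previous maximum severity, counts.

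| Subject | Records | As written | Linked |
|---|---|---|---|
| A | Headache, severe at −6 h, mild at +20 h | TEAE, iv | Not a TEAE |
| B | Infusion site pain, moderate at 30 h, mild at 80 h | TEAE, iv and po | TEAE, iv |
| C | Nausea, mild at −5 h, moderate at +10 h | TEAE, iv | TEAE, iv |
| D | Nausea, moderate at 90 h | TEAE, po | TEAE, po |
| E | Headache, moderate at −4 h, unchanged | Not a TEAE | Not a TEAE |

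Subjects with any TEAE / iv / po: as written 4 / 3 / 2, linked 3 / 2 / 1. Linking removes only A's TEAE and B's po entry. C, who worsened after dosing, is kept.

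**4. Illustrative size**

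N per arm = 670 / 2 = 335 (SAP 5.1, 1:1 randomization). All rates below are assumptions.

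- Added to the po table = 335 × (share with an iv-phase AE) × (share of these stepping down on oral drug).
  - Low: 335 × 0.10 × 0.10 = 3.4 (1 percentage point)
  - Middle: 335 × 0.20 × 0.30 = 20.1 (6 points)
  - High: 335 × 0.20 × 0.50 = 33.5 (10 points)
- Spurious TEAEs = 335 × (share with a pre-dose AE that improves after dosing and no other TEAE of that term).
  - 335 × 0.01 = 3.4; 335 × 0.03 = 10.0; 335 × 0.05 = 16.8

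**The case against.** The strongest reply has five parts.

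- **The once-per-term rule already deals with this.** It does for the overall TEAE tables, including those by severity and relationship and the infusion-site table, whenever onset is after first dose. A reader might infer that every improving AE is counted as a new TEAE; the documents do not support that. The rule does not reach a pre-dose onset or the separate po table.
- **The definition governs and the start-date sentence only sets the timing.** That is a fair reading for pre-dose AEs, and under it the case disappears. The programmer would then have to compare each record with its predecessor, and the SAP gives no way to do so. The fields it names for the AE listings include no continuation flag, although eCRF instructions, which are not in the documents, might supply one.
- **The period assignment does not contradict the TEAE definition.** Correct. An iv-onset AE that eases on oral drug is a genuine TEAE, and the definition is silent on period. The fault there is that a step-down is dated as an onset.
- **The affected set is small.** Partly so. The pre-dose window is short, conditions ongoing at consent go to medical history (Protocol 8.3), and non-serious worsening of the pneumonia is recorded as clinical failure rather than an AE (Protocol 8.21.5).
- **The iv/po split is supplementary.** Protocol 12.9.1 does not list it, neither document says it is meant to isolate the safety of each formulation, and listings will show dates and severity. This lowers the priority, but the SAP plans the table and it should count what it says it counts.

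**Conclusion.** The point holds as a defect in written counting rules. The po-period table is the more material case: no text in either document prevents an easing iv-onset AE from entering it. The pre-dose case is narrower and arises because two adjacent sentences in SAP 10.1 give different answers for the same record.

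The size is unknown. Under the assumed rates, about 3–34 of 335 per arm would be added to the po table, and about 3–17 per arm would gain a spurious TEAE. The po range is calculated on all 335 and falls if many subjects never switch. A reader might suppose that everyone moves to oral drug, but the switch is optional and depends on stability criteria. Subjects who already have a po-period TEAE of the same term would add nothing either.

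A reader might also infer a bias between arms. The documents do not show one: both arms follow the same rule, and no arm-specific AE rates are given. Efficacy, sample size and alpha are untouched. The correction is worth making, but no primary conclusion depends on it.

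**What to change.** In SAP 10.1:

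1. Link each record opened for a change in severity to its parent event, by a continuation flag if one is collected, otherwise by the same preferred term with contiguous stop and start dates.
2. Use the parent's onset date and time for TEAE status and for iv or po period.
3. Let a later record qualify in its own right only if its severity exceeds the pre-dose maximum (for TEAE status) or the prior maximum (for period). Accepting any increase would be too loose: an AE that goes from moderate before dosing to mild, then back to moderate after dosing, never exceeded its pre-dose level.
4. Reword the start-date sentence so that it implements the definition before it.

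The cost is one paragraph and one derivation, with no new data if records are linked by term and dates. The downside is some uncertainty in linking where dates are partial and imputed under SAP Appendix 3.

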10.2 Vital Signs

Blood pressure (systolic and diastolic), respiratory rate, temperature, and pulse/heart rate will be summarized using descriptive statistics at the following time points: Day 1 to Day 14,, ECR Visit, EOT Visit, PTE Visit, and highest and lowest post-baseline value. Heart rate and blood pressure will also be summarized for the following additional time points: 30 minutes before and approximately 1 hour after the completion of the infusions on Day 1 and Day 2. Descriptive statistics of the change from baseline to each post-baseline time point and the highest and lowest post-baseline value will also be provided. Baseline is defined as the value closest to but prior to the initiation of test article administration. If no value is available prior to the initiation.

Post-baseline vital signs will be defined as clinically notable (CN) if they meet the criterion value or both the criterion value and the change from baseline criterion listed in Table 9. The incidence of CN vital signs will be summarized by time point and treatment group and will be listed and flagged in by-subject listings. The overall post-baseline incidence of CN values for each vital sign parameter, which includes values from unscheduled post-baseline visits, will also be summarized. A listing will also be provided of subjects with a CN vital sign and will list all values for a vital sign noted as CN.

Vital Sign Parameter	Flag	Criterion Value	Change from Baseline
Systolic Blood Pressure	High (CH)	≥ 180	Increase of $\geq 20 \text{ mmHg}$
(mmHg)	Low (CL)	≤ 90	Decrease of $\geq 20 \text{ mmHg}$
Diastolic Blood Pressure	High (CH)	≥ 105	Increase of $\geq 15 \text{ mmHg}$
(mmHg)	Low (CL)	≤ 50	Decrease of $\geq 15 \text{ mmHg}$
Hoort Data (hnm)	High (CH)	≥ 120	Increase of ≥ 15 bpm
Heart Rate (bpm)	Low (CL)	≤ 50	Decrease of ≥ 15 bpm
Tomporatura (0C)	Low (CL)	<36.0	NA
Temperature (°C)	High (CH)	>38.0	NA

 Table 9.
 Criteria for Treatment Emergent Clinically Notable Vital Signs

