## 6.2 Inclusion Criteria

Each subject must meet all of the following criteria to be enrolled in this study:

- 1. Written and signed informed consent must be obtained before any protocol specific assessment is performed.
- 2. Male or female, aged 18 years or older.
- 3. Has at least 3 of the following symptoms:
  - Cough
  - Production of purulent sputum
  - Dyspnea (shortness of breath)
  - Pleuritic chest pain
- 4. Has at least TWO of the following abnormal vital signs:
  - Fever or hypothermia documented by the investigator (temperature > 38.0°C [100.4°F] or < 36.0°C [95.5°F])
  - Hypotension with SBP < 90 mm Hg
  - Heart rate > 90 beats per minute (bpm)
  - RR > 20 breaths/minute
- 5. Has at least 1 clinical sign or laboratory finding associated with CABP:
  - Hypoxemia ( $PaO_2 < 60 \text{ mm Hg by ABG or oxygen saturation} < 90\%$  by pulse oximetry)
  - Physical examination findings of pulmonary consolidation (eg, dullness on percussion, bronchial breath sounds, or egophony)
  - An elevated total white blood cell (WBC) count (> 12,000 cells/mm^3) or leucopenia (WBC < 4,000 cells/mm^3) or elevated immature neutrophils (> 15% band forms) (regardless of total peripheral WBC count)
- 6. Has disease categorized as being PORT Risk Class III or IV at Screening (see PORT Risk Class calculation in Appendix 5).
- 7. Radiographically-confirmed pneumonia, ie, new or progressive pulmonary infiltrate(s) on chest X-ray (CXR) or chest computed tomography (CT) scan consistent with acute bacterial pneumonia within 48 hours prior to the first dose of test article.

- 8. Is expected to require a minimum of at least 2 days of iv therapy for the initial treatment of CABP.
- 9. Females must have a negative pregnancy test at Screening and agree to comply with using an acceptable method of birth control as per your local requirements (eg, abstinence, po contraceptive, intrauterine device [IUD], barrier contraception [condom], tubal ligation, hysterectomy, bilateral oophorectomy, postmenopausal or vasectomized partner) from Screening through PTE. Males must agree to use an acceptable method of birth control with female partner(s) and must not donate sperm from Screening through PTE.

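### Read literally, the SAP 10.2 rule for clinically notable vital signs never uses the Table 9 change limits for blood pressure and heart rate; the rule should be stated parameter by parameter

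*SAP*

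**What the plan says.** SAP 10.2 defines a post-baseline vital sign as clinically notable "if they meet the criterion value or both the criterion value and the change from baseline criterion listed in Table 9". Table 9 is captioned "Criteria for Treatment Emergent Clinically Notable Vital Signs". Its limits are:

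| Parameter | High | Change for high | Low | Change for low |
|---|---|---|---|---|
| Systolic BP (mmHg) | ≥180 | rise ≥20 | ≤90 | fall ≥20 |
| Diastolic BP (mmHg) | ≥105 | rise ≥15 | ≤50 | fall ≥15 |
| Heart rate (bpm) | ≥120 | rise ≥15 | ≤50 | fall ≥15 |
| Temperature (°C) | >38.0 | NA | <36.0 | NA |

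On use, the SAP says "The incidence of CN vital signs will be summarized by time point and treatment group". It adds an overall count that takes in unscheduled values, and listings. Protocol 12.9.2 gives no rule of its own and leaves the criteria to the SAP.

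**The concern.** A change column is normally there to separate an abnormality that arose on treatment from one the subject brought into the trial. The sentence that applies Table 9 does not make use of it.

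This matters more here than in a healthy population. Inclusion Criterion 4 (Protocol 6.2) requires at least two of four abnormal vital signs, and three of the four overlap with Table 9:

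- The temperature cut-offs are the same in both places.
- A systolic pressure below 90 at entry already meets the Table 9 low limit of ≤90.
- Heart rate above 90 qualifies with no upper limit, so a baseline of 120 or more is possible.

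A subject who enters beyond a limit and is recovering can therefore be flagged until the value comes back inside it. A single such reading also puts the subject into the overall post-baseline count. At stake is whether the table shows what its caption promises, and whether two programmers working from the same SAP would produce the same numbers.

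**Working it through.** There is no stated figure to reproduce; the check is of the rule itself.

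**1. Logic.** Let A be 'criterion value met' and B be 'change criterion met'. The sentence as written is A OR (A AND B).

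| A | B | As written | A alone | A AND B |
|---|---|---|---|---|
| no | no | no | no | no |
| no | yes | no | no | no |
| yes | no | yes | yes | no |
| yes | yes | yes | yes | yes |

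The third and fourth columns agree in every row, so B has no influence. The two readings differ in the third row, where the value is beyond the limit but the change is too small or in the other direction.

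**2. Examples against Table 9** (values chosen for illustration).

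| Parameter | Baseline → later | Change | As written | Both required |
|---|---|---|---|---|
| Heart rate | 128 → 121 | −7 | flagged | not flagged |
| Heart rate | 132 → 124 | −8 | flagged | not flagged |
| Systolic BP | 82 → 88 | +6 | flagged | not flagged |
| Heart rate | 112 → 121 | +9 | flagged | not flagged |
| Heart rate | 105 → 124 | +19 | flagged | flagged |
| Systolic BP | 128 → 88 | −40 | flagged | flagged |
| Temperature | 39.6 → 38.4 | −1.2 | flagged | flagged (change is NA) |

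The first three subjects are improving. The fourth has newly crossed the limit, but by less than the listed change ("Increase of ≥ 15 bpm"), so the choice of reading affects more than abnormalities present at entry.

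**3. Every integer pair of baseline and later value.** The ranges are arbitrary: systolic 70–220 (151 values), diastolic 30–130 (101), heart rate 40–160 (121).

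- Flags as written = (number of later values beyond a limit) × (number of baseline values).
  - Systolic: (41 + 21) × 151 = 9,362.
  - Diastolic: (26 + 21) × 101 = 4,747.
  - Heart rate: (41 + 11) × 121 = 6,292.
- Flagged pairs that were beyond the same limit at baseline and have since moved back towards it = k(k − 1)/2 for k values beyond each limit.
  - Systolic: 820 + 210 = 1,030.
  - Diastolic: 325 + 210 = 535.
  - Heart rate: 820 + 55 = 875.

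| Parameter | Pairs | As written | Both required | Difference | Of which improving |
|---|---|---|---|---|---|
| Systolic BP | 22,801 | 9,362 | 7,092 | 2,270 | 1,030 |
| Diastolic BP | 10,201 | 4,747 | 3,507 | 1,240 | 535 |
| Heart rate | 14,641 | 6,292 | 4,637 | 1,655 | 875 |

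The rule as written never differed from the criterion value alone. With both conditions required, no improving pair is flagged. These are counts of cells on a grid. They show that the readings diverge; they do not estimate how many patients are involved.

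**4. Comparison within the SAP.** For adverse events, SAP 10.1 uses treatment-emergent to mean new, more frequent or worse. SAP 10.3 pairs a QTcF at or below a threshold at baseline with one above it later. SAP 10.4 uses grade shifts and bases its transaminase and bilirubin percentages on subjects normal at baseline. The vital-sign flag, read literally, is the one threshold summary of the three that ignores baseline.

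**The case against.** The best defence is Table 9 itself. Its change column is filled for three parameters and NA for temperature. Read together with the sentence, this suggests that the value alone decides where no change is listed and that both conditions apply elsewhere. The 'or' then has a purpose and the heart-rate example of 128 to 121 is not flagged. That reading is plausible and probably intended. It does not settle the matter, because the SAP nowhere states it and a programmer following the sentence would count differently. It also leaves temperature unchanged: a resolving entry fever is still flagged.

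Second, the body of SAP 10.2 speaks only of clinically notable values; treatment-emergent appears only in the caption, and the new-or-worse definition is written for adverse events. That is fair. For temperature, what remains is a mismatch between caption and content.

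Third, the direction of change is visible elsewhere. SAP 10.2 also plans change-from-baseline summaries at each time point and at the extremes, incidence by time point, and a listing of all values of any sign found notable. This limits the harm considerably.

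A reader might go further and infer that the table would consist mostly of pneumonia at entry, or would hide a difference between the drugs. The documents do not support that:

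- They give no baseline distribution of vital signs.
- Entry needs a heart rate above 90, while Table 9 needs 120 or more.
- Respiratory rate can qualify a subject but is not in Table 9, and diastolic pressure is in Table 9 but is not an entry criterion. A subject with heart rate 95 and respiratory rate 22 satisfies Inclusion Criterion 4 without any Table 9 abnormality.
- Exclusion Criterion 12 removes subjects who need acute drug support of blood pressure.
- The same rule applies to both randomised, blinded arms, so no direction of bias follows.

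**Conclusion.** The point holds as a defect of wording that changes counts. Taken literally, the change limits for systolic pressure, diastolic pressure and heart rate have no effect, and improving values that began beyond a limit enter a table captioned as treatment emergent. The sensible alternative reading is not stated, and the two readings disagree whenever a value is beyond its limit without the listed change.

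The consequence is small. It is confined to descriptive safety tables and listings and does not touch the primary analysis. The literal rule would bring in some disease present at entry and may dilute the contrast between arms. How much cannot be derived, because it depends on how many subjects have baseline values beyond the Table 9 limits and how long these persist, and neither is given.

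**What to change.** Replace the sentence in SAP 10.2 with a rule by parameter, for example:

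> Systolic pressure, diastolic pressure and heart rate are clinically notable only when the Table 9 criterion value and the Table 9 change from baseline are both met. Temperature, for which no change is listed, is judged on the criterion value alone.

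For temperature, then do one of two things: remove the treatment-emergent label, or keep the overall count and show beside it the subjects whose baseline did not meet the criterion. The overall count should not be restricted to subjects with a baseline inside the limits. That would leave a rise from 38.2 to 40.5 °C unflagged, although the fever worsened.

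The cost is one sentence, a caption or one extra table row, and the matching programming specification. No new data are needed, since SAP 7.2 and 10.2 already define the baseline value.
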